Appendix 27 - Caregiver Survey

CAL	REG	HVER	OUEST	IONNA	IRE

Please complete this questionnaire to the best of your abilities and return it in the enclosed postage-free envelope. If you have questions about the survey, you can contact a COMPASS Study Team Member at [name].

- 1. During the past 3 months, did you help the stroke/TIA survivor with activities like preparing meals, shopping, getting and/or taking medications, scheduling and/or getting to doctor's appointments.
 - f O Yes, I helped with these activities ightarrow **PROCEED TO QUESTION 2**
 - O No, I did not help with these activities

IF NO, did someone else help? O Yes	O No, the stroke survivor did not need help with these activities
You may stop the survey, please mail t	his survey back. Thank you for your time!

2.	How are you related to the stroke survivor? I am his/her	r	
0	Spouse O Neighbor or friend O Brother or sister	r O Parent or legal guardian	O Daughter or son
0	Other, please specify		
	Since your loved one or friend was discharged from the bacare for him/her? (check only one)	nospital following his/her stroke, w	nat is the total length of time you provided
0	I have been providing care ever since he/she came home	O I provided care for 5-6 weeks	O I provided care for 11-12 weeks
0	I provided care for 1-2 weeks	O I provided care for 7-8 weeks	
0	I provided care for 3-4 weeks	O I provided care for 9-10 weeks	
4.	At the time you were providing the most care, how many	y hours per week did you spend pro	oviding care?

O Less than 10 hours per week O 10-19 hours per week O 20-29 hours per week O 30 or more hours per week

5. At any time over the past 3 months, have you provide the fo		nce with ctivities?		need help nis assistance?	Did you als this before	
	YES	NO	YES	NO	YES	NO
Bathing/showering	0	0	0	0	0	0
Dressing	0	0	0	0	0	0
Getting out of bed/chair	0	0	0	0	0	0
Helping to/from bathroom	0	0	0	0	0	0
Feeding	0	0	0	0	0	0
Preparing Meals	0	0	0	0	0	0
Shopping	0	0	0	0	0	0
Laundry	0	0	0	0	0	0
Handling Finances	0	0	0	0	0	0
Assistance with housework	0	0	0	0	0	0
Assisting with yardwork /house or car maintenance	0	0	0	0	0	0
Scheduling appointments (doctors, rehab, home health, etc.)	0	0	0	0	0	0
Transportation to pharmacy and medical appointments	0	0	0	0	0	0
Transportation to grocery store, places around town, etc.	0	0	0	0	0	0
Using Medication	0	0	0	0	0	0

If yes, please describe:	100 1 0 0 0 0 0 0 0 0 0 0 0 0 0 0 0 0 0			
7. Does anyone else provid	de care for this stroke survivor? O Yes O No			_
If YES, please indicate v	who these people are and how they are related to the stroke survivor. (Ch	eck all that apply)		
O Spouse	O Neighbor or friend			
O Brother or sister	O Parent or legal guardian			
O Daughter or son	O Other, please specify			
		Yes, on a	elp you think a	
		regular basis	sometimes	No
My sleep is disturbed (light)	For example: the person I care for is in and out of bed or wanders around at	0	0	0
Caregiving is inconveniently help.)	ient (For example: helping takes so much time or it's a long drive over to	0	0	0
Caregiving is a physica required.)	d strain (For example: lifting in or out of a chair; effort or concentration is	0	0	0
Caregiving is confining	(For example: helping restricts free time or I cannot go visiting.)	0	0	0
There have been family privacy.)	v adjustments (For example: helping has disrupted my routine; there is no	0	٥	0
There have been chang on vacation.)	es in personal plans (For example: I had to turn down a job; I could not go	0	0	0
7. Does anyone else provide care for this stroke survivor? O Yes O No If YES, please indicate who these people are and how they are related to the stroke survivor. (Check all that apply) O Spouse O Neighbor or friend O Brother or sister O Parent or legal guardian O Daughter or son O Other, please specify 8. Below is a list of things that other caregivers have found to be difficult. For each item, please fill in ONE bubble that indicates how often you have found this difficult. We have included some examples that are common caregiver experiences to help you think about each item. Your situation may be slightly different, but the item could still apply. Yes, on a regular basis sometimes Yes, on a regular basis sometimes Yes, on a regular basis sometimes O O O Caregiving is inconvenient (For example: helping takes so much time or it's a long drive over to help.) Caregiving is a physical strain (For example: lifting in or out of a chair; effort or concentration is O O O Caregiving is confining (For example: helping restricts free time or I cannot go visiting.) There have been family adjustments (For example: helping has disrupted my routine; there is no privacy.) There have been family adjustments (For example: I had to turn down a job; I could not go				
	onal adjustments (For example: severe arguments about caregiving.)	0	0	0
There have been emotion		0	0	0
Some behavior is upset	the person reale for accuses people of taking timigs.)		0	0
Some behavior is upset remembering things; or t It is upsetting to find th	he person I care for has changed so much from his/her former self (For	0	100000	
Some behavior is upset remembering things; or to the sample: he/she is a different to the sample: he/she is a different to the sample: he/she is a different to the sample to the sample.	the person I care for has changed so much from his/her former self (For ferent person than he/she used to be)	20-50	0	0
Some behavior is upset remembering things; or to the example: he/she is a difference have been work.	he person I care for has changed so much from his/her former self (For ferent person than he/she used to be) adjustments (For example: I have to take time off for caregiving duties.)	0	86	

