Fewer than 50% of individuals with stroke have their risk factors assessed, treated, or controlled. Of those overweight at initial evaluation, 90% remain overweight. Nearly half of hypertensive individuals do not have blood pressure controlled. Smokers do not quit and few participate in exercise programs. At three months post-discharge, only 75% of stroke patients are still taking their preventive medications. About 40% remain dependent on others. Stroke also affects caregivers. Caregivers have poorer mental health, less social contact and activity, and are at increased risk for depression.

Comprehensive post-acute services for stroke require bridging hospital-based acute care with expanded care teams for rehabilitation, primary care management, access to community resources, and caregiver support. Evidence-based reviews have concluded that stroke morbidity and mortality could be reduced through effective transitional care, ^{22–24} secondary prevention, ²⁵ and rehabilitation early post-stroke. ²⁶ Involvement with a stroke liaison worker or case manager is associated with more knowledge about stroke and satisfaction with services. ^{27,28} Caregiver-oriented, individualized discharge planning for stroke patients going home improves caregiver preparedness. ²⁹

Given the significant impact of stroke on public health, the high risk and complexity of these patients early after discharge, and the strain on caregivers, an effective post-acute care model is needed. A pragmatic trial is the ideal method to test a care model that can be readily disseminated and implemented.

Objectives & Specific Aims

The COMprehensive Post-Acute Stroke Services (COMPASS) Study will determine the effectiveness of a post-acute comprehensive intervention.

Primary Study Question:

Does implementation of the COMPASS for stroke patients discharged directly home, improve functional outcomes (measured by the Stroke Impact Scale-16) at 90 days post-stroke? Intention-to-treat principles will be used to determine all primary and secondary outcomes.

Primary Aim:

Comparative effectiveness of COMPASS verses usual care (Control) on stroke survivor functional status (measured by the Stroke Impact Scale) at 90 days post-stroke.

Secondary Aims:

- 1) Using responses from the 90 day caregiver survey, determine if the COMPASS intervention reduces caregiver strain (measured by the Modified Caregiver Strain Index) at 90 days post-stroke.

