Data collected to support the operations of the trial.	Discharge Data	Resources and stroke education materials, assess for rehabilitation, ambulatory status, Rankin Score, final diagnosis, discharge disposition, ICD-10 data, etc.	Entered into the COMPASS Database by the hospital	9

March 19, 2021 Application - IRB00035998 Patient Participant Study Outcomes (Phase 2):

Ancillary Study General Heath and PROMIS Global-10 @90 days, consenting 23 Function patients asked by CSRL		Measure	Assessment(s)	When Collected	Appendix
	Ancillary Study		PROMIS Global-10	patients asked by	23

March 19, 2021 Application - IRB00035998 Caregiver Participant Study Outcomes (Phase 1 only):

	Measure	Assessment(s)	When Collected	Appendix
Secondary Outcome	Caregiver Burden	Modified Caregiver Strain Index	@95 days, mailed to the caregiver	27
Data collected to support the operations of the trial.	Relation to stroke patient	Relation to stroke patient	@95 days, mailed to the caregiver	27
Data collected to support the operations of the trial.	Demographics	Age, Gender, Race	@95 days, mailed to the caregiver	27
Data collected to support the operations of the trial.	Primary Caregiver	Are you the primary caregiver	@95 days, mailed to the caregiver	27
Data collected to support the operations of the trial.	Length of Caregiving service	How long have you been providing care? How many hours per day do you spend providing care? Do others help provide care?	@95 days, mailed to the caregiver	27
Data collected to support the operations of the trial.	Type of caregiving activities	Type of caregiving activities	@95 days, mailed to the caregiver	27
Data collected to support the operations of the trial.	Awareness and use of Community Resources	Awareness and use of Community Resources	@95 days, mailed to the caregiver	27
Data collected to support the operations of the trial.	Self-rated General Health	Compared to others your age, how would you rate your health using a scale of 1 to 5, with 1 being "Poor" and 5 being "Excellent?"	@95 days, mailed to the caregiver	27
Data collected to support the operations of the trial.	Accessed the COMPASS Website	Have you explored the information on the COMPASS website	@95 days, mailed to the caregiver	27

Study outcomes collected and linked to insurance claims data (Phase 1 & Phase 2):

	Measure	Assessment(s)	When Collected	Appendix

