For secondary aims and outcomes measured on a continuous scale, we will use a similar approach as above (i.e. for the Modified CSI). For binary outcomes such as whether a patient is readmitted within 30 or 90 days (Secondary Aim 2), we will use mixed logit models to fit the relationship between the intervention and outcome measures. The mixed logit model is similar to the mixed model presented above but uses a logit link in a generalized linear mixed model. Software is

Application - IRB00035998

readily available (e.g., SAS PROC GLIMMIX) that can fit these models. The mixed logit model approach will also allow a mixture of fixed and random effects to be included as in the mixed model above. Other Secondary Aim 2 variables will be analyzed using a mixed model or alternatively generalized linear mixed models (e.g., Poisson regression [with overdispersion] for the number of inpatient days).

We will examine 1-year mortality rates as a binary outcome and use the methods described above to compare groups, but we will also consider mortality as a time-to-event outcome and compare groups using Cox proportional hazards models. In these survival analysis models, the treatment indicator will be included as the primary independent variable and the stratum included as stratification factor.

Human Subjects Protection

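### Caregiver strain is scored only for caregivers who gave some help in the past three months, a post-randomisation condition that COMPASS may change, so the planned comparison is not between the randomised groups and its bias has no known direction

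*Protocol*

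**What the plan says.** Secondary aim 1 of the protocol is to "determine if the COMPASS intervention reduces caregiver strain", measured by the Modified Caregiver Strain Index. Under Primary Study Question the protocol states that "Intention-to-treat principles will be used to determine all primary and secondary outcomes". The outcome table gives the timing of the index as "95 days, mailed to the caregiver", for Phase 1 only.

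Question 1 of the survey (Appendix 27) asks whether the caregiver helped over the past three months with tasks such as meals, shopping, medicines and appointments. A caregiver who ticks "No, I did not help with these activities" is asked whether someone else helped, the alternative being "No, the stroke survivor did not need help with these activities". Either way the survey ends there. The strain items are question 8. Question 3 accepts a total of one to two weeks of care, so a caregiver who helped briefly and then stopped still reaches question 8.

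On analysis, the Analytical Plan says: "For secondary aims and outcomes measured on a continuous scale, we will use a similar approach as above (i.e. for the Modified CSI". The approach referred to is a mixed model with stratum and arm as fixed effects and hospital as a random effect. No score, estimand or sensitivity analysis is given for caregivers who stop at question 1. The supplied SAP covers claims and mortality only. Its sections 2 and 6.4 refer to a Phase 1 SAP that is not among the documents.

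**The concern.** The aim is about caregiver strain in the randomised arms. The available scores describe strain among caregivers who gave some help, and that group is formed after randomisation.

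COMPASS could change who is in it. The coordinator arranges follow-up appointments before discharge, reviews medicines and appointments on the day 2 call, and coordinates referrals at the 7-14 day visit. The sample care plan (Appendix 20) points to meal, transport and medication services. These overlap with the tasks listed in question 1. The population is mild (mean NIH stroke score 3.2 in the Study Population section, with TIA eligible), so caregivers close to the line between helping and not helping are plausible.

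If the share or mix of helpers differs by arm, the difference in mean strain combines any effect on strain with a change in who is measured. A benefit could then be hidden, reversed or manufactured.

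**Working it through.** The documents give no expected mean, SD, effect size, power or number of caregivers for this endpoint, so there is no stated figure to reproduce. The check is whether the selection can change the sign, and under what conditions. **All inputs below are assumed, in arbitrary units.**

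**Model.** Control-arm helpers are a share L of light helpers (mean mL) and 1 - L heavier helpers (mean mH). COMPASS stops a share r of light helpers from ever helping and lowers strain by a fraction k in those who still answer.

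- Control mean = L·mL + (1 - L)·mH
- COMPASS total, T = (1 - k)[L(1 - r)·mL + (1 - L)·mH]
- Helpers-only COMPASS mean = T / (1 - L·r)
- All-caregiver COMPASS mean, non-helpers scored 0 = T

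The all-caregiver figure is per control-arm helper. Adding caregivers who would help in neither arm shrinks it in proportion and does not change its sign.

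**1. Light help prevented altogether.** L = 0.5, mL = 2, mH = 8, r = 0.3, k = 0.

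- Control mean = 0.5×2 + 0.5×8 = 5.00
- T = 0.35×2 + 0.5×8 = 4.70
- Helpers-only mean = 4.70 / 0.85 = 5.53, difference **+0.53** (apparent harm)
- All-caregiver difference = 4.70 - 5.00 = **-0.30** (benefit)

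Over L from 0.3 to 0.7 and r from 0.05 to 0.5, with k = 0, the helpers-only difference is +0.06 to +1.00 and the all-caregiver difference is -0.03 to -0.70.

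**2. How easily this is cancelled.** The fall in strain among remaining helpers that brings the helpers-only difference to zero is 1 - (control mean / helpers-only mean at k = 0). In the case above it is 1 - 5.00/5.53 = 9.6%. Over L from 0.3 to 0.7 it is 1.0% to 1.7% at r = 0.05, 4.1% to 7.2% at r = 0.2, and 10.7% to 20.3% at r = 0.5.

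**3. The filter as written: any help in three months.** Keep L = 0.5, r = 0.3, k = 0. Let q be the share of relieved light helpers who gave no help at all and so skip question 8. The rest helped early, stopped, and answer with strain f·mL, where f runs from 0 to 1.

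| q | Helpers-only difference | All-caregiver difference |
|---|---|---|
| 0 | -0.30 to 0.00 | -0.30 to 0.00 |
| 0.25 | -0.12 to +0.12 | -0.30 to -0.08 |
| 0.5 | +0.08 to +0.24 | -0.30 to -0.15 |
| 1 | +0.53 | -0.30 |

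At q = 0 the two differences are equal for every f, so there is no selection bias.

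**4. Opposite direction.** If COMPASS draws in 10% more light helpers (r = -0.1), the helpers-only mean is (0.55×2 + 0.5×8)/1.05 = 5.10/1.05 = 4.86, difference -0.14. At 30% more it is 5.30/1.15 = 4.61, difference -0.39. On the all-caregiver scale strain rises by 0.10 (5.10 - 5.00) and 0.30 (5.30 - 5.00), so the helpers-only result is a false benefit.

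**The case against.** A reader might infer that strain is measured only in caregivers who are still helping at the survey, so that light helpers relieved by COMPASS drop out and the bias runs against the intervention. The form does not support this. Question 1 covers any help in three months, and a caregiver who helped for one or two weeks is scored. For selection of that kind, COMPASS must prevent help over the whole period, yet after discharge it acts first on day 2 and then at days 7-14. This narrows the concern considerably. It does not remove it, because appointment scheduling begins before discharge and some caregivers may be spared helping from the outset.

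The direction is also open. COMPASS adds a clinic visit, and question 1 counts arranging or getting to appointments as help, so light helpers could be drawn into the COMPASS arm. The protocol also allows a direct caregiver assessment at that visit. This objection stands in full.

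A third point is that the Phase 1 SAP may already say how a caregiver who stops at question 1 is scored, and the protocol names a model without saying that these caregivers are excluded. That cannot be checked here. It is a caveat: in the supplied documents, these caregivers have no score and no rule gives them one.

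**Conclusion.** The concern holds in a limited form. Modified CSI scores exist only for caregivers who gave some help in the past three months, a post-randomisation condition that COMPASS may change. The planned mixed model on those scores is therefore not a comparison of the randomised groups, despite the intention-to-treat statement.

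The documents do not establish the size or sign of the bias. It can hide or reverse a benefit if COMPASS prevents light help entirely, show a false benefit if COMPASS brings in light helpers, or be absent if relieved caregivers helped early and then stopped. The figures above show only that a sign change is possible. They rest on assumed helper shares, mean strain and relief rates. Because the direction is unknown, a reader could not correct a helpers-only result by judgement. The point affects the interpretation of secondary aim 1 and not the primary endpoint.

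**What to change.** Before the caregiver data are analysed by arm, pre-specify three things:

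- **(a)** Report by arm the proportion of returned surveys that answer no at question 1, split into someone else helped and no help needed, with a mixed logit model for giving any help.
- **(b)** Add a companion mixed-model analysis over all returned surveys, scoring no help needed as zero strain. For someone else helped, give a sensitivity range, for example zero and values imputed from helpers.
- **(c)** Interpret the helpers-only result only beside (a) and (b).

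The cost is analysis wording and some extra output, since the form already records the reason for a no answer. There are two limits. Zero strain for non-helpers is an assumption, and return of the survey is itself a post-randomisation event, so the companion analysis is not free of selection either. All results should therefore be shown together. If the Phase 1 SAP already contains such a rule, citing it in the protocol is enough.

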Appendix 28 - Proxy SIS-16

Removed – COMPASS is no longer asking caregiver's questions about the patient. The Proxy SIS-16 has been removed.

Appendix 30 - Caregiver Thank You Note

Removed – COMPASS will no longer be sending a 10 dollar gift card to caregivers.

Appendix 32 - DSMB Template Sections

List of Report Sections

- 1. Executive Summary
- 2. Protocol Synopsis
 - a. Project Organizational Chart
 - b. Study Purpose
 - c. Projected Timetable And Schedule
 - d. List Of Participating Hospitals
- 3. Narrative & Trial Summary
 - a. Study Status
- 4. Recruitment And Randomization
- 5. Training
- 6. Implementation Of The Compass Study And Assessment Of Fidelity
- 7. Vanguard Hospital
- 8. Safety And Privacy Of Participants
- 9. Outcomes
- 10. Publications
- 11. Contract Modifications
 - a. Recommendations From The DSMB
 - b. Summary Of Protocol Changes
- 12. Recruitment And Participant Status: Figures & Tables
 - a. Hospital Recruitment And Randomization
 - b. Participant Enrollment And Outcome Ascertainment
- 13. Data Quality Tables
 - a. Study Activity Completion
 - b. Quality Analysis Of Implementation
 - c. Summary Of Data Form Completion
- 14. Appendices
 - a. Bimonthly Survey For Implementation Site Webinars With Post-Acute Coordinators (Pac) And Advanced Practice Providers (App)
 - b. Monthly Performance Report Templates
 - c. Bimonthly Survey For Implementation Site Webinars With Home Health And Outpatient Rehabilitation Teams
 - d. List Of Publications And Presentations For Compass

Appendix 33 - CTSI Supplemental Proposal (Implementation of COMPASS)

Implementation of an evidence-based chronic disease care model: Identifying individual, organizational, and community facilitators ([name] / [name])

RESEARCH PLAN

Specific Aims:

Aim 1. Evaluate the Reach, Adoption, Implementation, and Maintenance (RE-AIM) of the COMPASS intervention, an evidence-based chronic disease care management model.

Aim 2. Identify individual, organizational, and community factors that facilitate or are challenges to implementation of COMPASS.

Aim 3. Identify strategies to build, maximize, and sustain community resource networks working together with the local hospital-based post-acute care coordination teams to support local implementation of COMPASS.

Design & Methods

Study Design: We will capture quantitative data via (1) bi-weekly questionnaires to the hospital-based post-acute care (PAC) teams and Home Health Outpatient Therapy (HHOP) Teams to capture perceived barriers to uptake, and (2) real-time data on enrollment and performance measures at each site. We also will capture qualitative data via (1) transcription and coding of bi-weekly phone calls with PAC teams, and HOPP team and (2) semi-structured interviews with the Director of Implementation for the COMPASS study and members of the Implementation Committee. These calls will be facilitated by the Director of Implementation for the COMPASS study ([name]) and will allow post-acute care coordinators to problem-solve together. These 4 data sources, collected from 20 health systems over one year, will identify which patient, staffing, and community-level factors drive intervention uptake, challenges to uptake, and how health systems can improve performance on pre-defined performance measures.

Sample: In the COMPASS study, 41 hospitals have been randomized (stratified by stroke volume and primary stroke center status) to receive COMPASS or usual care (control group). The proposed pilot will include the 20 hospitals randomized to receive COMPASS. Roll-out of these 20 intervention sites has occurred in 3 waves (n=5, n=5, n=10), starting in August 2016. Within each wave, hospitals trained together and started implementation at the same time; they also participate in bi-monthly problem-solving calls together. We are adapting strategies after each wave to meet health systems' unique environments and optimize approaches accordingly.

Measurement Framework: The RE-AIM Framework, developed by Glasgow et al (1999), will guide the process evaluation of the implementation of COMPASS. RE-AIM guides the assessment of the **Reach**, **Effectiveness**, **Adoption**, **Implementation**, and **Maintenance** of public health interventions (e.g., policy or programmatic). **Table 1** defines the RE-AIM components for COMPASS. **Table 2 (Appendix)** shows how the RE-AIM framework will guide the proposed process evaluation. Re-Aim has been used to evaluate the implementation of other large trials (e.g., ATTEND https://clinicaltrials.gov/ct2/show/NCT02123875).

Table 1. RE-AIM Components Defined for COMPASS

Reach	Effectiveness	Adoption	Implementation	Maintenance
of intended		by target staff,	consistency, and	of intervention effects
population		settings, or	adaptations made	in individuals and
		institutions	during delivery	settings over time

Application - IRB00035998

**				
The absolute number,	The impact of	The absolute number,	The intervention	The extent to which
proportion, and	COMPASS on	proportion, and	agents' fidelity to the	COMPASS becomes
representativeness of	important outcomes,	representativeness of	various elements of	institutionalized or
patients who are	including potential	hospitals and	an intervention's	part of the routine
enrolled in	negative effects,	clinicians who are	protocol, including	organizational
COMPASS at	quality of life, and	willing to initiate	consistency of	practices and policies
hospital discharge	economic outcomes	COMPASS	delivery as intended	
			and the time and cost	
			of the intervention	

Data Collection: In this mixed methods design, we will collect quantitative data via (1) bi-weekly questionnaires to the hospital-based post-acute care (PAC) teams and HHOP teams to capture perceived barriers to uptake (see **Appendix** for survey), and (2) how well the clinic is actually implementing the new care model (i.e., real-time data on enrollment and performance measures). We also will capture qualitative data via (1) transcription and coding of bi-weekly phone calls with PAC teams and HHOP Calls (2) semi structured interviews with the Director of Implementation for the COMPASS study and members of the Implementation Committee (see **Table 3**). The bi-weekly calls are facilitated by the Director of Implementation for the COMPASS study ([name]) and allow PAC teams across the state to problem-solve together. These 4 data sources, collected from 20 health systems over one year, will allow us to triangulate which patient, staffing, and community-level factors drive intervention uptake, which pose challenges to uptake, and which drive health systems' ability to improve performance.

Table 3. Data Sources

Quantitative Data Source	Qualitative Data Source
Bi-weekly questionnaires to the hospital-based post-acute care (PAC) and HHOP teams to capture perceived barriers to uptake	Transcription of bi-weekly phone calls with PAC and HHOP teams to problem solve barriers to uptake
Real-time data on patient enrollment	Semi-structure interviews with the Director of Implementation for the COMPASS study ([name], RN)
Real-time data on 6 performance measures	Semi-structured interviews with members of the COMPASS Implementation Committee

Quantitative Data Analysis: Descriptive statistics (e.g., frequencies) will be used to aggregate questionnaire responses.

Qualitative Data Collection and Analysis: PAC team phone calls and interviews with the Director of Implementation and members of the Implementation Committee will be audio recorded and transcribed verbatim by Accukey Transcription (vendor #25466). Transcripts will be de-identified and verified by study investigators. Transcripts will be imported into NVivo for data management and analysis. The transcripts will be coded independently by members of the research team including the PI and Co-PI, and a graduate student research assistant (RA) trained in qualitative research methods. Initially, phone calls and interviews will be coded using open coding procedures as described by Charmaz (2006) and Ryan and Bernard (2003). The research team will meet to discuss the codes identified in the data. Codes will be sorted and categorized into themes that represent the factors that affect implementation (e.g. challenges, facilitators, and strategies). A coding schema will be developed collaboratively by the PI, Co-PI ([name] / [name]), and student RA. This schema will be used to code subsequent team meeting transcripts. The coders will meet regularly (monthly) to discuss the ongoing coding and resolve discrepancies. Major themes will be reported with supporting quotations. Credibility of analysis will be enhanced by (1) independent coding; (2) examination of negative cases and situations of considerable agreement or disagreement; (3) qualitative assessment of agreement between coders over time; and (4) discussing the major themes with the PACs in the 3 Waves to get input and feedback (member checking). Our analysis will also include cross-comparisons of subgroups (urban/rural sites, large/small volume sites) to determine differences within a heterogeneous population of health systems.

Table 4. Mapping the RE-AIM framework (Glasgow et al 1999) to the proposed process evaluation

Table 4. Mapping the RE-AIM framework (Glasgow et al 1999) to the proposed proces	5 ev	aiuai	1011		
	Reach	Effectiveness*	Adoption	Implementation	Maintenance
Characteristics of enrolled patients (age, language, sex, race, Hispanic, insurance, diagnosis, aphasia, ambulatory status at discharge, NIH stroke score)	Х				
PM1. Receipt of follow-up telephone call within 2 business days of hospital discharge				Χ	
PM2. Receipt of follow-up visit within 7 to 14 days of hospital discharge				Χ	
PM3. Receipt of e-Care plan during follow-up clinic visit				Χ	
PM4. Receipt of all home health and outpatient rehabilitation services (including physical therapy, occupational therapy, and speech and language therapy) prescribed at hospital discharge, 2-day follow-up call, or 7-14-day follow-up clinic visit by 30-days after hospital discharge				х	
PM5. Receipt of all home health rehabilitation services (including physical therapy, occupational therapy, and speech and language therapy) prescribed at hospital discharge, 2-day follow-up call, or 7-14-day follow-up clinic visit by 30-days after hospital discharge				Х	
PM 6. Receipt of all outpatient rehabilitation services (including physical therapy, occupational therapy, and speech and language therapy) prescribed at hospital discharge, 2-day follow-up call, or 7-14-day follow-up clinic visit by 30-days after hospital discharge				Х	
Characteristics of enrolled health systems (size, location, Comprehensive Stroke Center certification)			Х		
Characteristics of PAC teams (number of FTE, license, etc)			Х		
Characteristics of Community Resource Networks			Χ		
Characteristics of clinical staff participating in bi-weekly problem solving calls			Х		
Challenges with enrollment, 2 day call, 14 day visit, e care plan, receipt of therapy, community resource network, administrative tasks				Х	
Requests for additional training				Х	
Time it takes to integrate COMPASS components into system (ramp up)					Х
What are sites doing to maintain COMPASS? What are they changing? Are they returning to their original model of care?					Х
*90-day outcomes and claims data are part of the COMPASS trial, not this pilot		*X			
PM = Performance Measure	1		1	1	

March 19, 2021 Application - IRB00035998 Appendix 34 – 2Day Disposition Form

ID Number:	Form Code: C D S P Date: 07JUN2016 Version 1.0
ADMINISTRA	Date: Day
Did you c hospital?	complete a follow-up call with the patient or caregiver after the patient was discharged from the
	s → Go to Q1a
□ No	→ Go to Q1b
	Month Day Year
2b. Reas	son for no follow-up call:
	□ Did not attempt call
	☐ Could not reach patient/caregiver after 2 attempts
	□ Patient/caregiver refused
	 □ Patient/caregiver could not complete (e.g. confused, unable to communicate, too sick, etc.) □ Patient/caregiver did not have workable number
	☐ Patient hospitalized
	☐ Patient transferred to a skilled nursing facility
	□ Patient deceased
	□ Other (specify)
	END OF 2-DAY CALL DISPOSITION FORM

March 19, 2021 Application - IRB00035998 Appendix 35 – Clinic Disposition Form

	Clinic Visit Disposition Form Form Code: V D S P Date: 10Feb2017 Version 2.0
ADMINISTE 0a. Completio	RATIVE INFORMATION (0a-0c are auto-populated) n Date: Day
1. Was the	e follow-up clinic visit conducted?
□ Y	es → Go to Q1a
□N	o → Go to Q1b, then END OF FORM
1a. Dat	e of clinic visit:
1b. If n	o visit was completed, select reason:
	 □ Visit NOT scheduled: Patient prefers to follow-up with his/her own PCP or another doctor □ Visit NOT scheduled: Patient reported that he/she is too sick or disabled to attend □ Visit NOT scheduled: Patient cannot afford to attend the scheduled visit □ Visit NOT scheduled: Patient does not have transportation □ Visit NOT scheduled: Patient reported that he/she lives out of the area and doesn't want to travel
	 □ Visit was scheduled, but patient did not attend Transportation Issues No insurance coverage for visit Conflicting medical appointment
	Patient/caregiver preferred not to drive a long distance for the follow-up visit Patient cancelled No show / reason unknown Other:
	□ Patient transferred to nursing home □ Patient hospitalized □ Patient deceased □ Other
	e Stroke Caregiver Assessment triggered by the Post-Stroke Functional Assessment? es → Go to Q2a
_ 11	*

2a. Was it performed?	
□ Yes	
\square No \rightarrow Go to Q2b	
2b. Why not?	
□ Primary caregiver not present□ Primary caregiver refused	
3. Was the eCare Plan generated?	
 □ Yes, electronically on the iPad → Go to Q3a □ No → Go to Q3b 	
3a. Was the eCare Plan printed and shared with the patient?	
□ Yes	
□ No	
3b. Reason for no eCare Plan:	
☐ Acute change of patient's status requiring emergent care	
☐ Technical error / server problem	
☐ Clinic workflow wouldn't allow generation of eCare Plan	
□ Other	
4. Is the patient in need of any rehabilitation services that they are not currently receiving?	
☐ Yes → Go to Q4a	
□ No	
4a. What referrals were made after the clinic visit (check all that apply)?	
☐ Home health PT ☐ Outpatient PT	
☐ Home health OT ☐ Outpatient OT☐ Home health SLP☐ Outpatient SLP☐	
5. Were referrals made to any pharmacy-based services?☐ Yes → Go to Q5a	
□ No	
 5a. Which services (check all that apply)? ☐ Community Care of North Carolina (CCNC) pharmacy network ☐ Local pharmacy outside of the CCNC pharmacy network ☐ Free clinic with on-site pharmacist ☐ Hospital-based pharmacist follow-up 	
Clinic Visit Disposition Form	Page 2 of 3

6 Were referral	s made to community resources such as Area Agency on Aging, support groups, etc.	
(check all that	t apply?)	
□ Yes →	Go to Q6a	
□ No		
	community services (check all that apply)?	
	Adult Services/Social Support Services Stroke Support Group	
	Counseling Services for stress, depression (e.g. CareNet)	
	Chronic Disease Management Programs	
	Community Exercise Programs Falls Prevention Programs	
	Nutrition Assistance Programs	
	Aphasia Support Group	
	Smoking Cessation Program Transportation Services	
	Caregiver Support Services	
	Other Services:	
o 	END OF CLINIC VISIT DISPOSITION FORM	
	END OF CLINIC VISIT DISPOSITION FORM	
	END OF CLINIC VISIT DISPOSITION FORM	_
	END OF CLINIC VISIT DISPOSITION FORM	_
	END OF CLINIC VISIT DISPOSITION FORM	_
	END OF CLINIC VISIT DISPOSITION FORM	
	END OF CLINIC VISIT DISPOSITION FORM	_
	END OF CLINIC VISIT DISPOSITION FORM	_
	END OF CLINIC VISIT DISPOSITION FORM	_
	END OF CLINIC VISIT DISPOSITION FORM	_
	END OF CLINIC VISIT DISPOSITION FORM	_
	END OF CLINIC VISIT DISPOSITION FORM	_
	END OF CLINIC VISIT DISPOSITION FORM	_
	END OF CLINIC VISIT DISPOSITION FORM	
	END OF CLINIC VISIT DISPOSITION FORM	
	END OF CLINIC VISIT DISPOSITION FORM	
	END OF CLINIC VISIT DISPOSITION FORM	

March 19, 2021 Application - IRB00035998 Appendix 38 – Phase 2Enrollent Form

COMPAS COMPREHENSIVE POST-ACI	Dautiain and Envallment Fauna	
ID Number:		Version 2.0 (Phase 2)
ADMINISTRATIVE INFORM	MATION (auto-populated)	
0a. Completion Date:	/ Day / Pear Ob. Staff ID:	
0c. NCSCC ID:	Od. Hospital ID: Of.	Form Status:
A. PATIENT CONTACT IN	FORMATION	
Patient full name	First Middle	Last
2. Telephone number(s)		
a. Primary number: (
	lome □ Mobile □ Work □ Other Veekday daytime □ Weekday evening □ Weekend □ Anytime	
b. Alternate 1: ()	
	lome ☐ Mobile ☐ Work ☐ Other	
Best time to call: □ V	Veekday daytime ☐ Weekday evening ☐ Weekend ☐ Anytime	
c. Alternate 2:)	
505	lome Mobile Work Other	
Best time to call: $\square V$	Veekday daytime ☐ Weekday evening ☐ Weekend ☐ Anytime	 
4. Home address	Address line 1	
7	Address line 2	
(Dity State Zip	County
Participant Enrollment Form v2.0 for Ph	uase 2	Page 1 of 5

	re a caregiver (i.e., a family memb g meals, shopping, getting or takir		
appointments).			
□ Yes □ No	□ Don't know		
C. ADDITIONAL CO	ONTACT INFORMATION		
□ Patient unable or	unwilling to provide an additional	contact / not documented	→ Go to Question 16
12. Full name			_
10 T	First	Middle	Last
13. Telephone numb			
a. Primary numbe	rr: ()		
Тур	e: 🗆 Home 🗆 Mobile 🗆 Work	□ Other	
b. Alternate 1:	()		
